### **8.2.1.3 End-of-Treatment and Follow-up Tumor Imaging**

For participants who discontinue study intervention, tumor imaging should be performed at the time of treatment discontinuation ( $\pm$ 4 week window). If previous imaging was obtained

within 4 weeks prior to the date of discontinuation, then imaging at treatment discontinuation is not mandatory. For participants who discontinue study intervention due to confirmed disease progression, this is the final required tumor imaging if the investigator elects not to implement iRECIST.

For participants who discontinue study intervention without confirmed disease progression, every effort should be made to continue monitoring disease status by tumor imaging using the same imaging schedule used while on treatment (Q12W until Week 54 after C1D1 [ $\pm 7$  days], Q24W thereafter or sooner or more frequently if required by local standard of care, until disease progression per RECIST 1.1) until the start of a new anticancer treatment, disease progression, pregnancy, death, withdrawal of consent, or the end of the study, whichever occurs first.

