Poststudy Anticancer Therapy						X	X	X	All anticancer therapy will be recorded until time of death or termination of Survival Follow-up. If a clinic visit is not feasible, follow-up information may be obtained via telephone or e-mail.

Study Period	Screening Phase	Intervention Phase (Q3W)			End of Treatment	Post-treatment Follow-up			Notes
		1	2	3 and onwards		Safety Follow-up a	Follow-up b	Survival Follow-up	
Treatment Cycle					Discontinuation				Procedures should occur predose on Day 1 of each cycle unless otherwise noted.  Post-treatment Period: Refer to Section 8.12.3.
Scheduled Timing	-28 to -1				At time of d/c	30 days post last dose		~Q12W (telephone)	
Window (days):		+ 3	± 3	± 3		+ 7	± 7	± 7	
Survival Status		<----->						X	After investigator-determined PD or start of new anticancer treatment. In addition, upon Sponsor request, participants may be contacted for survival status at any time during the course of the study (unless this information is not allowed to be provided due to confidentiality).
Efficacy Procedures									
Tumor Imaging (CT/MRI; Chest, Abdomen, and Pelvis)	X	<-----> c			X d			X	Prior scans performed within the screening period but before signing informed consent may be used if consistent with protocol requirements per SIM. All imaging visits have a scheduling window of ±7 days. Imaging to be performed Q12W or sooner if clinically indicated from the date of C1D1 until Week 54 of study treatment, Q24W or sooner if clinically indicated thereafter, or more frequently if required by local standard of care until disease progression per RECIST 1.1.

Study Period	Screening Phase	Intervention Phase (Q3W)			End of Treatment	Post-treatment Follow-up			Notes
		1	2	3 and onwards		Safety Follow-up a	Follow-up b	Survival Follow-up	
Treatment Cycle					Discontinuation				Procedures should occur predose on Day 1 of each cycle unless otherwise noted.  Post-treatment Period: Refer to Section 8.12.3.
Scheduled Timing	-28 to -1				At time of d/c	30 days post last dose		~Q12W (telephone)	
Window (days):		+ 3	± 3	± 3		+ 7	± 7	± 7	
Safety Procedures									
Height	X	X	X	X	X				Pediatric height to be measured at every visit. Adult height measured at Screening only.
Weight	X	X	X	X	X				To be measured at every visit.
Full Physical Examination	X								Within 7 days prior to C1D1.

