### **8.2.1.2 Tumor Imaging During the Study**

The first on-study scan should be performed at 12 weeks (84 days  $\pm$ 7 days) from the date of allocation. Subsequent tumor scans should be performed every 12 weeks (84 days  $\pm$ 7 days) or more frequently if clinically indicated. After 54 weeks (378 days  $\pm$ 7 days), participants who remain on treatment will have scans performed every 24 weeks (168 days  $\pm$ 7 days). Scan timing should follow calendar days and should not be adjusted for delays in cycle starts. Scans are to be performed until disease progression is identified by the investigator or notification by the Sponsor, or until the start of new anticancer treatment, withdrawal of consent, or death, whichever occurs first.

Objective response should be confirmed by a repeat scan performed at least 4 weeks after the first indication of a response is observed. Participants will then return to the regular scan schedule, starting with the next scheduled time point. Participants who receive additional scans for confirmation do not need to undergo the next scheduled scan if it is fewer than 4 weeks later; scans may resume at the subsequent scheduled time point.

On-study brain or bone scans should be performed if clinically indicated or to confirm CR (if other lesions indicate CR and brain or bone lesions existed at baseline).

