### **8.12.3 Discontinued Participants Continuing to be Monitored in the Study**

#### **8.12.3.1 Safety Follow-up Visit**

The mandatory Safety Follow-up Visit should be conducted approximately 30 days after the last dose of study intervention or before the initiation of a new anticancer treatment, whichever comes first. If the EOT visit occurs  $\geq 30$  days after the last dose of study intervention, a Safety Follow-up Visit is not required. In this situation, all procedures required at the 30-day Safety Visit and EOT are performed once and entered into the EOT visit only.

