### 9.6.1.2 Duration of Response (DOR)

The non-parametric Kaplan-Meier method will be used to estimate the DOR survival curve. Only the subset of participants with confirmed CR or PR response verified by BICR will be included in the analysis. 95% CIs for the median response duration and point estimates at various follow-up times will be calculated. The censoring rules for the analysis of DOR are summarized in [Table 8](#).

Table 8 Censoring Rules for Analysis of DOR

Situation	Date of Progression or Censoring	Outcome
No progression nor death, no new anticancer therapy initiated	Last adequate disease assessment	Censor (non-event)
No progression nor death, new anticancer therapy initiated	Last adequate disease assessment before new anticancer therapy initiated	Censor (non-event)
Death or progression immediately after $\geq 2$ consecutive missed disease assessments or after new anticancer therapy, if any	Earlier date of last adequate disease assessment prior to $\geq 2$ missed adequate disease assessments and new anticancer therapy, if any	Censor (non-event)
Death or progression after $\leq 1$ missed disease assessments and before new anticancer therapy, if any	Progressive disease or death	End of response (Event)
DOR=duration of response Note: A missed disease assessment includes any assessment that is not obtained or is considered inadequate for evaluation of response.		

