### 9.6.1.3 Progression-free Survival

The non-parametric Kaplan-Meier method will be used to estimate the PFS survival curve. 95% CIs for the median PFS and PFS point estimates at various follow-up times from the first day of study treatment will be calculated.

Since disease progression is assessed periodically, PD can occur any time in the time interval between the last assessment where PD was not documented and the assessment when PD is documented. The true date of disease progression will be approximated by the earlier of the date of the first assessment at which PD is objectively documented per RECIST 1.1 by BICR and the date of death. Death is always considered a PD event. Participants who do not

experience a PFS event will be censored at the last disease assessment. The censoring rules for the analysis of PFS are summarized in [Table 9](#). If a participant meets multiple criteria for censoring, the censoring criterion that occurs earliest will be applied.

Table 9 Censoring Rules for Analysis of PFS

Situation	Date of Progression or Censoring
PD or death documented after $\leq 1$ missed disease assessment, and before new anticancer therapy, if any	Progressed at date of documented PD or death
PD or death documented immediately after $\geq 2$ consecutive missed disease assessments or after new anticancer therapy, if any	Censored at last disease assessment prior to the earlier date of $\geq 2$ consecutive missed disease assessment and new anticancer therapy, if any
No PD and no death; and new anticancer treatment is not initiated	Censored at last disease assessment
No PD and no death; new anticancer treatment is initiated	Censored at last disease assessment before new anticancer treatment
PD=progressive disease; PFS=progression-free survival	

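### Nothing asks that the end-of-treatment scan precede new anticancer therapy, so some progressions may be censored at an older scan, pulling PFS and DOR upward by an unknown and possibly small amount

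*Combined protocol and SAP*

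**What the plan says.** **Timing of the scan.** Section 8.2.1.3 states that "tumor imaging should be performed at the time of treatment discontinuation", with a window of plus or minus 4 weeks. It waives the scan if there was one "within 4 weeks prior to the date of discontinuation, then imaging at treatment discontinuation is not mandatory". The imaging row of the Schedule of Activities (Section 1.3) says: "All imaging visits have a scheduling window of ±7 days".

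**Link to new therapy.** Routine on-study scanning runs to progression "or until the start of new anticancer treatment, withdrawal of consent, or death, whichever occurs first" (Section 8.2.1.2). The second paragraph of Section 8.2.1.3 sets a similar end for follow-up scans. The one visit timed against a switch is the Safety Follow-up Visit, due about 30 days after the last dose "or before the initiation of a new anticancer treatment, whichever comes first" (Section 8.12.3.1). That section does not mention imaging.

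**Censoring.** For a participant with new therapy and neither progression nor death, Table 9 (PFS) gives "Censored at last disease assessment before new anticancer treatment" and Table 8 (DOR) gives "Last adequate disease assessment before new anticancer therapy initiated". Both tables also censor progression or death occurring after new therapy, at the last assessment before it (or before two or more missed assessments, if that is earlier). Section 9 specifies no PFS or DOR analysis that ignores new therapy.

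**The concern.** Take a participant who stops treatment without progression on a scan read centrally and soon starts something else. Whether progression counts may then depend on which came first, the scan or the new drug, and the protocol leaves that order open for up to 4 weeks after the stop. Participants who switch quickly are more likely than others to be progressing, so censoring them is not neutral.

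With one arm there is no comparator in which a similar bias could offset. Section 4.2 makes durable response by central review part of what is to support the postmarketing requirement, and Table 10 lists DOR under key secondary. The two stated scan windows also disagree, whatever the bias.

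**Working it through.** **1. The plan's own figure.** The documents give no figure for this effect. The only sizing figure is the Clopper-Pearson interval for 28 responders of 50. The lower limit is the 2.5% quantile of Beta(28, 23) = 41.3% and the upper limit is the 97.5% quantile of Beta(29, 22) = 70.0%, a half-width of 14.4 points. This matches Table 11 and does not depend on the scan rule.

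**2. Who is exposed.** Under Section 8.2.1.5 and Table 6, clinically unstable participants stop at the first radiologic progression and stable ones when it is confirmed. A progression scan then predates the switch and is an event if central review agrees. The remainder are stops without centrally documented progression: participant request, adverse events or investigator judgement (Section 7.1), a need for prohibited treatment (Section 6.5, where stop and switch can nearly coincide), or investigator-assessed progression that central review does not confirm.

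**3. One case.** Assume scans at Weeks 12, 24, 36, 48 and 72, reading the change to 24-week intervals as falling after Week 48, and no unscheduled scan. Last scan Week 48; stop Week 68; new therapy Week 70; end-of-treatment scan Week 71 shows progression.
- Under Section 8.2.1.3 the window is Weeks 64 to 72, so the scan complies. Table 9 censors at Week 48, which is 71 − 48 = 23 weeks before the progression scan.
- Had the scan been done at Week 69, before new therapy, PFS would be an event at Week 69.
- Under the Schedule's 7 days the window would be Weeks 67 to 69.

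**4. Bracket by hand.** Section 2.2.1.3 gives PFS of 52% at 12 months and 48% at 24 months in the earlier single-arm pembrolizumab study. For illustration, apply these to 50 participants with no other censoring: 26 are event-free at 12 months. Let k of the 24 earlier events become censored. The Kaplan-Meier estimate is lowest if all k are censored at baseline, 26/(50 − k), and cannot exceed (26 + k)/50.

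| k (assumed) | Lowest | Highest |
|---|---|---|
| 0 | 52.0% | 52.0% |
| 2 | 26/48 = 54.2% | 28/50 = 56.0% |
| 4 | 26/46 = 56.5% | 30/50 = 60.0% |
| 6 | 26/44 = 59.1% | 32/50 = 64.0% |

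The 24-week gap applies to few events on this curve: (0.52 − 0.48) × 50 = 2 between 12 and 24 months. Censoring only those two leaves 12-month PFS at 52% and lifts 24-month PFS from 48% to at most (24 + 2)/50 = 52%.

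**5. Simulation with progression between scans.** 400,000 participants, piecewise-exponential PFS through 52% and 48%, the scan schedule of step 3 with 24-week intervals continuing, data cut at 36 months. A share f of events (assumed) arises with new therapy started before the end-of-treatment scan. As written, these are censored at the previous scan. Scan first means a scan within 1 week of progression and before new therapy. With waiver means the same, except that no scan is taken if one was done in the prior 4 weeks. At f = 0 the 12-month value is 54.7%, not 52%, because progression is dated at the next scan.

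| f | 12 mo: as written | scan first | with waiver | 24 mo: as written | scan first | with waiver |
|---|---|---|---|---|---|---|
| 5% | 56.3% | 54.6% | 55.3% | 50.3% | 48.5% | 49.2% |
| 10% | 57.9% | 54.5% | 55.8% | 52.0% | 48.5% | 49.8% |
| 20% | 61.3% | 54.2% | 56.9% | 55.7% | 48.4% | 51.0% |
| 30% | 65.0% | 54.0% | 58.1% | 59.7% | 48.4% | 52.3% |

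The 12-month excess is 56.3 − 54.6 = 1.7 points at 5%, 61.3 − 54.2 = 7.1 at 20%, and 65.0 − 54.0 = 11.0 at 30%. About 64% of progressions fall more than 4 weeks after the last scan, so the waiver does not reach them; the median age of that scan is 5.9 weeks. At f = 20%, ordering the scan while keeping the waiver removes (61.3 − 56.9)/7.1, about 62% of the excess. DOR was not simulated; Table 8 censors in the same way, so the direction is the same.

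**6. Against sampling error.** At 52% with 50 participants, the approximate 95% half-width is 1.96 × √(0.52 × 0.48/50) = 13.8 points.

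**The case against.** The protocol has safeguards. Scans may be brought forward when clinically indicated, and unscheduled scans that show progression should go to central review (Section 8.2.1), so a participant who is visibly deteriorating should often be scanned before any switch. Most stops for progression follow a progression scan. The Schedule places end-of-treatment imaging at discontinuation, and the Safety Follow-up Visit that comes later must itself precede new therapy, so the usual sequence already puts the scan first. The 4-week window can be read as a specific rule overriding a general one. PFS and DOR are secondary and there is no hypothesis test.

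Much of this stands, and it confines the problem to a subset. It does not close the gap: none of these provisions orders the scan before the switch, and the Schedule says its 7 days apply to all imaging visits.

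Three stronger readings are tempting, and the documents support none of them.
- A reader might infer that PFS and DOR are inflated across the study. That needs a known, sizeable share of affected participants, and no such figure is given.
- A reader might infer that every affected case lengthens the estimates. A participant who stops for an adverse event without progressing, and is censored at an older clean scan, only loses follow-up; the estimate can fall slightly.
- A reader might infer that the end-of-treatment scan lapses once new therapy starts. That cut-off is written for routine and follow-up scans; the sentence requiring the end-of-treatment scan carries none.

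**Conclusion.** The point holds for a defined subset: participants who stop without centrally documented progression and start new therapy before the end-of-treatment scan. Tables 8 and 9 then censor them at a scan up to about 12 weeks old before Week 54 and about 24 weeks old after it (before visit windows), even if the later scan shows progression or the participant dies. Where they are progressing, the censoring is informative and the net pull on PFS and DOR is upward.

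The size cannot be established from the documents. The illustrations rest on assumed shares, on the earlier study's PFS curve, and on every affected participant progressing; they show direction and scale, not an estimate. The effect is zero if nobody switches before the scan, and at low shares it is well inside the sampling error. ORR and the sample size are unaffected. The two scan windows need reconciling in any event.

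**What to change.** 1. In Section 8.2.1.3 and footnote d of the Schedule of Activities, state that for participants stopping without radiographic progression, the already required end-of-treatment scan should, where feasible and without delaying treatment, be obtained before the first dose of new anticancer therapy, with the reason recorded if it is not. The existing 4-week waiver can stay.
2. Reconcile the plus or minus 4 weeks in Section 8.2.1.3 with the plus or minus 7 days in the Schedule.
3. Add PFS and DOR sensitivity analyses that count progression or death regardless of new anticancer therapy, because the waiver and the censoring rule leave some bias after step 1. These cannot recover a scan that was never taken, so they complement step 1 and do not replace it. While drafting them, reconcile the text of Section 9.6.1.3, which treats every death as an event, with Table 9, which censors death after new therapy.

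Cost: slightly tighter scan scheduling for some participants and one extra analysis per endpoint. No scan is added, because this one is already required.

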#### **8.2.1.4 RECIST 1.1 Assessment of Disease**

RECIST 1.1 will be used by BICR as the primary measure for assessment of tumor response, date of disease progression, and as a basis for all protocol guidelines related to disease status (eg, discontinuation of study intervention). Although RECIST 1.1 references a maximum of 5 target lesions in total and 2 per organ, this protocol allows a maximum of 10 target lesions in total and 5 per organ, if clinically relevant to enable a broader sampling of tumor burden.

[Figure 2](#) illustrates the imaging flow involving verification of PD for clinically stable participants.

#### **8.2.1.5 iRECIST Assessment of Disease**

iRECIST is based on RECIST 1.1, but adapted to account for the unique tumor response seen with immunotherapeutic drugs. iRECIST will be used by the investigator to assess tumor response and progression, and make treatment decisions. When clinically stable, participants should not be discontinued until progression is confirmed by the investigator, working with local radiology, according to the rules outlined in Appendix 8. This allowance to continue treatment despite initial radiologic PD takes into account the observation that some participants can have a transient tumor flare in the first few months after the start of immunotherapy, and then experience subsequent disease response. This data will be captured in the clinical database.

Clinical stability is defined as the following:

- Absence of symptoms and signs indicating clinically significant progression of disease
- No decline in ECOG performance status (or Lansky scale, if appropriate)
- No requirements for intensified management, including increased analgesia, radiation, or other palliative care

Any participant deemed clinically unstable should be discontinued from study intervention at site-assessed first radiologic evidence of PD, and is not required to have repeat tumor imaging for confirmation of PD by iRECIST.

If the investigator decides to continue treatment, the participant may continue to receive study intervention and the tumor assessment should be repeated 4 to 8 weeks later to confirm PD by iRECIST, per investigator assessment. Images should continue to be sent in to the iCRO for potential retrospective BICR.

If repeat imaging does not confirm PD per iRECIST, as assessed by the investigator, and the participant continues to be clinically stable, study intervention may continue and follow the regular imaging schedule. If PD is confirmed, participants will be discontinued from study intervention.

If a participant has confirmed radiographic progression (iCPD) as defined in Appendix 8, study intervention should be discontinued; however, if the participant is achieving a clinically meaningful benefit, an exception to continue study intervention may be considered following consultation with the Sponsor. In this case, if study intervention is continued, tumor imaging should continue to be performed following the intervals as outlined in Section 8 and submitted to the iCRO.

A description of the adaptations and iRECIST process is provided in Appendix 8, with additional details in the iRECIST publication [Seymour, L., et al 2017]. A summary of imaging and treatment requirements after first radiologic evidence of progression is provided in Table 6 and illustrated as a flowchart in Figure 2.

[figure not shown]
Table 6 Imaging and Treatment After First Radiologic Evidence of Progressive Disease

	Clinically Stable		Clinically Unstable	
	Imaging	Treatment	Imaging	Treatment
First radiologic evidence of PD by RECIST 1.1 per investigator assessment.	Repeat imaging at 4 to 8 weeks to confirm PD.	May continue study intervention at the assessment of the investigator and after the participant's consent.	Repeat imaging at 4 to 8 weeks to confirm PD per investigator's discretion only.	Discontinue treatment.
First radiologic evidence of PD by RECIST 1.1 per investigator assessment.	Repeat imaging at 4 to 8 weeks to confirm PD.	May continue study intervention at the investigator's discretion while awaiting confirmatory tumor imaging by site by iRECIST.	Repeat imaging at 4 to 8 weeks to confirm PD per investigator's discretion only.	Discontinue treatment.
Repeat tumor imaging confirms PD (iCPD) by iRECIST per investigator assessment.	No additional imaging required.	Discontinue treatment (exception is possible upon consultation with Sponsor).	No additional imaging required.	Not applicable.

	Clinically Stable		Clinically Unstable	
	Imaging	Treatment	Imaging	Treatment
Repeat tumor imaging shows iUPD by iRECIST per investigator assessment.	Repeat imaging at 4 to 8 weeks to confirm PD. May occur at next regularly scheduled imaging visit.	Continue study intervention at the investigator's discretion.	Repeat imaging at 4 to 8 weeks to confirm PD per investigator's discretion only.	Discontinue treatment.
Repeat tumor imaging shows iSD, iPR, or iCR by iRECIST per investigator assessment.	Continue regularly scheduled imaging assessments.	Continue study intervention at the investigator's discretion.	Continue regularly scheduled imaging assessments.	May restart study intervention if condition has improved and/or clinically stable per investigator's discretion. Next tumor imaging should occur according to the regular imaging schedule.

iCPD=iRECIST confirmed progressive disease; iCR=iRECIST complete response; iPR=iRECIST partial response; iRECIST=modified Response Evaluation Criteria in Solid Tumors 1.1 for immune-based therapeutics; iSD=iRECIST stable disease; iUPD=iRECIST unconfirmed progressive disease; PD=progressive disease; RECIST 1.1=Response Evaluation Criteria in Solid Tumors 1.1

Figure 2 Imaging and Treatment for Clinically Stable Participants Treated With Pembrolizumab After First Radiologic Evidence of PD Assessed by the Investigator

iRECIST=modified Response Evaluation Criteria in Solid Tumors 1.1 for immune-based therapeutics; PD=progressive disease; RECIST 1.1=Response Evaluation Criteria in Solid Tumors 1.1

